Tryptophan is a precursor of serotonin and melatonin, which are known to be involved in the regulation of various fundamental behavioural and physiological functions including sleep, wakefulness, circadian rhythms, cognition and even mood. Previous studies have reported that evening ALAC supplementation can effectively increase the TRP:LNAA ratio up to 130%. However, dose response studies for evening ALAC supplementation to identify the optimal dosage and time response to the ratio are yet to be explored.

Through this study we aim to be able to identify this optimal dosage of ALAC for further research and recommendations of this supplement in sleep and mood outcomes.

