Participants will be required to report to the university at 17:00 hrs with a fasting period 2.5 hrs before arrival (14:30 hrs). Upon their arrival, simple height and weight measures will be taken by the researchers. Within the first hour of arrival, a trained researcher will insert a cannula into a forearm vein of the participants for blood samples to be taken. Baseline blood and saliva samples will be collected before the experimental supplement consumption. Further, each participant will be provided the experimental ALAC protein shake and a Visual Analog Scale (VAS) -sensory evaluation questionnaire to assess the preference of the ALAC shake at immediately post consumption of the drink (T=0 mins). Participants will also complete a Visual Analog Scale VAS -GI symptoms questionnaire, at two time points i.e. baseline (T=0 mins) and 2hrs post supplement consumption i.e. (T= 120 mins). Small amounts of blood will be drawn (5 mL) at half an hour interval from the time of the supplement consumption (pre supplement and 90 mins, 120 mins, 180 mins and 210 mins post supplement). During the experimental protocol, from T=0 to T= 210 mins, the participants will be asked to relax in an environment consistent lighting and discouraged from using screens. A saliva swab collection will once again be repeated at 3 hrs (210 mins) post supplement consumption. A simple chronotype questionnaire will also be administered to all the participants at this stage. At the end of the study protocol i.e., **21:00hrs**, the participants will be screened for alertness via Karolinska Sleepiness Scale (KSS)(Appendix 4) to assess their ability to drive back home post the intervention and in the event a participant scores >6.8 on the KSS scale, alternate arrangements to travel back home or temporary sleeping arrangements at Deakin University Campus will be made to ensure the participant's safety. Participants will also be handed a boxed dinner meal before leaving the lab. This procedure will be replicated for each of the four visits made be every participant, during the intervention. Participants will also receive a reimbursement via \$100 gift card on successfully completing all 4 intervention sessions.

Wash-out

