8.3 Any participant follow-up

There is no planned follow up following the cessation of the study.

Participants will be provided with a copy of the research report after publication if this option is selected on the consent form

Please ensure your responses to Sections 9-12 comply with Deakin's Research Data Management procedure and accurately reflect the details you have included in your Research Data Management Plan (a compulsory document for all Deakin research).

9. Data Collection/Gathering:

9.1 What information are you going to collect/gather/generate? (as required in addition to that outlined in the HREA)

Please note that prior to the recruitment of the first participant, this clinical trial is to be registered within the ANZCTR.

Personal information

- Name

-Contact number

- Email address (to be sent electronic PLS and consent form, and if selected, publication of study)

Screening measures

- Participant age
- Habitual dietary intake prior to the intervention
- Sleep quality via PSQI questionnaire
- Dietary allergies

-Chronotype measures via morningness eveningness questionnaire (MEQ)

Outcome measures

- Biochemical measures (plasma amino acids and plasma melatonin)
- Palatability of ALAC supplement doses via VAS-GI symptoms questionnaire administered

-Preference of the ALAC supplement doses via VAS -sensory evaluation questionnaire administered

Data Collection

- Blood samples across five timepoints during each intervention session on each of the four separate lab visits i.e., all four supplement doses, to be collected.

-Saliva sample at two time points during each intervention session, on four separate occasions i.e., all four supplement doses to be collected.

9.2 Data collection/gathering techniques: How will you collect/gather the information? Will any third parties be involved in any aspects of recruitment or data collection?

Screening measures

Participant characteristics – age, training level, medication use, alcohol and caffeine consumption, travel history across time zones, recency of night shift work will be collected at baseline using a simple questionnaire (Appendix 1).

Sleep quality – Participants will be screened using the Pittsburgh Sleep Quality Index (Appendix 2) to ensure the participants do not face any pre-existing sleeping difficulties.

Diet Recall - Participants will be asked to record a 3 day diet recall using Easy Diet Diary (EDD) mobile app prior to their first lab visit.

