Outcome measures

Biochemical measures – Blood samples will be collected by a researcher with phlebotomy training across five-timepoints on each intervention day. Plasma amino acid analysis will then be completed at Deakin University through liquid chromatography triple-quadrupole mass-spectrometry.

Plasma melatonin will be assessed through enzyme-linked immunosorbent assay according to manufacturer's instructions.

Palatability and preference will be assessed through a validated VAS -GI symptoms and VAS- sensory evaluation questionnaire to gauge the palatability and acceptance of the different supplement doses.

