13.1 Please describe your outcome measures

Primary outcome measures include:

-Amino acid analysis (i.e., plasma TRP:LNAA ratio)

Secondary outcome measures include:

-Plasma melatonin

-Palatability, appetite, and preference of the different alpha-lactalbumin supplement dosages

14. For research involving an unapproved therapeutic good (such as a drug, device or biological): 14.1 Does this project involve an unapproved therapeutic good requiring a Clinical Trial Notification (CTN)? (See the Clinical Trials webpage for more information about CTNs)

 \boxtimes Yes – go to the next question.

□ No – skip to Section 15 (results, outcomes and future plans)

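### As listed, no blood is drawn in the first 90 minutes after the drink, so the onset of the TRP:LNAA rise is unseen at every dose and an earlier peak would be recorded at 90 minutes

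*Protocol*

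**What the plan says.** Section 8.1 (Intervention) fixes the blood draws at "pre supplement and 90 mins, 120 mins, 180 mins and 210 mins post supplement". The same sentence opens with a different rule: "Small amounts of blood will be drawn (5 mL) at half an hour interval from the time of the supplement consumption". Section 9.1 plans "Blood samples across five timepoints during each intervention session", and section 9.2 repeats the count, "across five-timepoints on each intervention day". The observation period in section 8.1 runs "from T=0 to T= 210 mins", and the cannula is placed before the drink.

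On purpose, section 4.2 says that dose-response studies "to identify the optimal dosage and time response to the ratio are yet to be explored". The research question in section 4.3 covers both dosage and timing, and hypothesis 2 predicts that higher doses keep the ratio raised for longer. The primary outcome in section 13.1 is "Amino acid analysis (i.e., plasma TRP:LNAA ratio"), with no sampling time, peak, time to peak or area named. The protocol gives no expected time to peak at any dose and no reason for starting post-dose sampling at 90 min.

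**The concern.** A trial that wants the time course of a response needs samples on the way up as well as on the way down. On the listed times the whole early phase falls between two draws. Three things follow.

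- The onset of the rise cannot be seen at any dose, whenever the peak falls. Duration above baseline, the subject of hypothesis 2, then has an observed end but no observed start.
- An observed time to peak cannot be earlier than 90 min.
- If a curve peaks before 90 min, the highest sample lies below the true peak, and a trapezoid area is too small.

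If peak time also differed by dose, the loss would differ by dose. That would alter the shape of the dose-response on which hypothesis 1 (a linear rise, then a plateau near 40 g) depends. Samples that were not drawn cannot be recovered in the analysis.

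**Working it through.** **1. Count of draws.** One pre-dose draw plus four listed post-dose draws makes 5, which agrees with sections 9.1 and 9.2. Half-hourly draws over 0-210 min would be 0, 30, 60, 90, 120, 150, 180 and 210, which is 8 and does not agree. The five-draw count therefore supports the list. The gaps on the list are 90, 30, 60 and 30 min, and the first is 90/210 = 43% of the window.

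**2. Assumed curves.** The protocol gives no curve and no peak time, so both are assumptions. The rise above baseline is taken as a Bateman curve, f(t) = [exp(-ke·t) - exp(-ka·t)] / peak, with peak time tp = ln(ka/ke)/(ka - ke) and ka/ke = 1.5, 3 and 6. The true peak is set to 1.

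Worked example, ka/ke = 3 and tp = 45 min:
- ke = ln 3/(2 × 45) = 0.01221 and ka = 0.03662 per min.
- Unscaled peak at 45 min: 0.5774 - 0.1925 = 0.3849. Unscaled value at 90 min: 0.3333 - 0.0370 = 0.2963.
- Highest listed sample: 0.2963/0.3849 = 77% of the peak.
- Scaled values at 0, 90, 120, 180 and 210 min: 0, 0.770, 0.568, 0.285 and 0.199. The trapezoid area is 34.6 + 20.1 + 25.6 + 7.3 = 87.6.
- True area 0-210 min: [(1 - 0.0770)/0.01221 - (1 - 0.0005)/0.03662]/0.3849 = 125.5. The ratio is 87.6/125.5 = 70%.

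**3. Results on the listed times, over the three shapes.**

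| True peak (min) | Highest sample, % of peak rise | Read at (min) | Trapezoid area 0-210, % of truth |
|---|---|---|---|
| 30 | 42-58 | 90 | 45-60 |
| 45 | 74-82 | 90 | 67-73 |
| 60 | 91-94 | 90 | 78-80 |
| 75 | 98-99 | 90 | 84-85 |
| 90 | 100 | 90 | 87-88 |
| 120 | 100 | 120 | 91-92 |
| 180 | 100 | 180 | 94-95 |

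Peaks up to about 100 min are read at 90 min.

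**4. Check with another family.** With [(t/tp)·exp(1 - t/tp)]^k, for k = 1 (broad) and k = 3 (narrow), the highest listed sample is 40-74% of the peak at tp = 45, 75-91% at 60, 95-98% at 75, and 100% at 90 or 120 min. The direction is the same, and narrow curves lose more.

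**5. Comparison between doses, under a further assumption.** Suppose 10 g peaks at 45-60 min and 40 g at 90-120 min.
- Peak: from 1 - 0.935/1 = 7% to 1 - 0.741/1 = 26% of the rise.
- Area: from 1 - 0.802/0.874 = 8% to 1 - 0.674/0.916 = 26%.

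If instead all doses peak between 90 and 120 min, the peak shares are 99-100%. For a given shape the area shares differ by about 4% (for example 0.878 against 0.916).

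**6. Scale.** These are shares of the rise, not of the ratio. With the 46% rise at the low end of section 4.1, losing 7-26% of it lowers the ratio by 0.07 × 0.46/1.46 = 2% to 0.26 × 0.46/1.46 = 8%. With the 130% rise at the high end, it lowers it by 0.07 × 1.30/2.30 = 4% to 0.26 × 1.30/2.30 = 15%.

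**The case against.** The strongest reply is that the harm is hypothetical. The protocol gives no time to peak. From 75 min onward the highest listed sample already shows at least 98% of the peak rise on Bateman curves (95% on the narrow alternative), and nothing in the document says that small doses peak earlier than large ones. This stands, and it makes the between-dose figures conditional.

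Second, no peak, time-to-peak or area endpoint is defined. Section 11.1 plans mixed models of dose and period, and a comparison of doses at one fixed sampled time is untouched by the gap. The timing in the research question could also mean when to take the supplement rather than when the curve peaks. This stands too, but section 4.2 speaks of a time response and hypothesis 2 of duration. For both, the unseen onset matters whatever the peak time.

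Third, a Bateman curve describes one absorbed substance, whereas the outcome is a quotient of amino-acid pools that both respond to a protein drink. That is a fair limit on the exact percentages. It does not affect the fact that 90 minutes are unsampled.

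Fourth, the schedule is unsettled: truly half-hourly draws would remove the gap. The explicit list and the two five-draw counts point the other way, but the wording has to be reconciled in any case. Section 8.1 also equates 3 hours with 210 min, and Figure 1 is too broken in the available copy to decide the matter.

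A reader might also infer that the second draw of each close pair is redundant and that the 120-min draw could simply be moved to 45 min. The calculations do not support that. It would open a new gap from 90 to 180 min: a peak at 130 min would lose 4-6% on the Bateman curves and 11% on the alternative family with k = 2, against 1% or less on the listed times. It would also separate the blood draw from the GI questionnaire at 120 min.

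**Conclusion.** The gap is in the text and is confirmed by the five-draw counts. Followed as listed, the schedule never observes the onset of the rise at any dose and cannot record a peak earlier than 90 min. That is a weakness in a trial that asks about time response and duration.

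The bias in dose comparisons is conditional. It needs a peak, time-to-peak or area summary and at least some peaks well before 90 min. Under the assumed curves and the assumed peak times of 45-60 min for 10 g and 90-120 min for 40 g, 10 g is understated relative to 40 g by roughly 7-26% of the rise in peak and 8-26% in area. It is small if every dose peaks at 90 min or later, and absent for a comparison at one fixed sampled time.

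A reader might infer that the schedule hides a plateau and pushes the chosen dose upward. The documents do not support that as a finding, because they give no peak time for any dose and no sign that smaller doses peak sooner.

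**What to change.** In section 8.1, when the half-hourly wording is reconciled with the listed times, keep the listed draws and add one early draw, for example at 45 min, through the cannula already in place. Update the five-timepoint count in sections 9.1 and 9.2, and Figure 1. Do not drop the 120-min draw to make room.

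On the Bateman curves of the working, the added 45-min draw raises the highest sample to 100% of the peak rise for a 45-min peak and 96-97% for a 60-min peak. The area rises to about 92% and 94-95% of the truth. In the assumed 10 g versus 40 g case, the relative understatement falls to 0-4% in peak (1 - 0.963/1) and 2-6% in area (1 - 0.945/0.965 to 1 - 0.916/0.975).

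Cost: 5 mL more blood per visit (from 5 × 5 = 25 mL to 30 mL) and 16 × 4 = 64 more samples to assay (from 16 × 4 × 5 = 320 to 384).

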It is hypothesized that nutrition interventions that act on altering the serum TRP:LNAA ratio levels could positively impact sleep (2). Dietary precursors such as ALAC have previously been found to increase the serum TRP:LNAA ratio by as much as 46 -130% and can further influence the rate of synthesis and function of neurotransmitters serotonin and melatonin(5, 6). Most of the existing literature surrounding ALAC and sleep is conducted amongst healthy trained participants or athletic population groups with regards to improving sleep efficiency (7-10). However, across these studies, varying doses ranging from 20 g to 60 g of alpha-lactalbumin (ALAC) were supplemented without clear indication of the rationale behind the dosage strategy. Additionally, while one study supplementing two separate 20 g ALAC doses at dinner meal and before bedtime found a positive outcome on morning after sleepiness (5); another study supplementing 20 g ALAC after morning exercise and 40 g ALAC before bedtime showed no significant difference in morning sleepiness measures (11). Hence, the specific effect of ALAC on

sleep architecture and the optimal timing of consumption has yet to be investigated and warrants further research.

Further, there exists no body of research surrounding the dose response effect of ALAC supplementation on serum TRP:LNAA ratio, independent of other factors such as glucose intake and carbohydrate rich poor protein (CRPP) diets. Literature suggests that the presence of other amino acids as well as glucose around the ALAC consumption can alter the serum TRP:LNAA ratio by further increasing the LNAA levels or by mechanisms such as insulin secretion that promotes the uptake of branched-chain amino acids into the muscle (1).

The proposed study aims to answer this question of identifying an optimal dose and time of evening alpha-lactalbumin (ALAC) supplementation to raise the serum TRP:LNAA ratio, without the influence of any other dietary factors such as glucose or other proteins.

4.2 A rationale/justification (i.e. how the research will fill any gaps, contribute to the field of research or contribute to existing or improved practice)

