The wash-out phase is defined as a period of minimum three days to limit any carry-over effect of the ALAC supplement on the serum Tryptophan:LNAA ratio before administering the next dose. This ensures that the experimental protein dosages are adequately separated. This period is defined based on previous literature which has observed that a gap of 1-3 days to be sufficient to reverse the effect of a single dose of tryptophan on TRP:LNAA ratio (17,18). During the wash-out period, the participants will be required to continue eating and training as per their usual routine. No supplement will be provided during this phase.

DAY	DOSE 1	WASHOUT			DOSE 2	WASHOUT			DOSE 3	WASHOUT			DOSE 4
		2	3	4	5	6	7	8	9	10	11	12	13
17:00	(i) E												
17:15 BASELINE	۱.				♦ Ĥ				♦ Ĥ				۲
17:30 SH	É				∲ ₿				€ġ				1
					٢				٢				۲
19:30 Ŭ	• 🖻				\\$				\\$				•[
20:00	٢				٢				٢				۲
20:30	 ♦ ∯ 								۱.				٢
	FE PN				E M				E D				SE J

Figure 1 -Graphical description of the study protocol. Example of a participant prescribed all 4 doses of alpha -lactalbumin supplement in random order and the measures taken at different time intervals.

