11.2 Please describe your matching and sampling strategies

There will be no requirement to create matched groups due to the repeated measures study design. Each participant will act as their own control.

11.3 Please outline how you will account for potential bias, confounding factors and missing information

Bias

- Double-blinded study

-The different α -lactal bumin dosages to be matched for taste. An external researcher is to provide participants with the supplement to ensure the research team remains blinded to the experimental dosage.

- Diet – As protein and carbohydrates can influence the TRP:LNAA ratio, participants will be asked to come in fasting for a period of 3 hrs before the alpha-lactalbumin supplement consumption.

- Light will be controlled for after the supplement consumption and screen usage or viewing will be restricted to limit the impact of light on endogenous melatonin levels

Missing values will not be substituted in any circumstance (missing or otherwise). There are no planned data cleaning processes, with raw values only to be analysed.

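### The last meal and training may differ, unrecorded, across the four visits; this can shift the pre-dose sample and adds avoidable noise to the dose contrasts

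*Protocol*

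**What the plan says.** - **Aim.** Section 4.1 sets out to find the dose and timing that raise the ratio "without the influence of any other dietary factors such as glucose or other proteins".
- **Diet as bias.** Section 11.3 lists diet under Bias and gives the reason: "As protein and carbohydrates can influence the TRP:LNAA ratio". The control that follows is that "participants will be asked to come in fasting for a period of 3 hrs before the alpha-lactalbumin supplement consumption".
- **Visit day.** Under Intervention, section 8.1 has participants "report to the university at 17:00 hrs with a fasting period 2.5 hrs before arrival (14:30 hrs"). Blood is drawn "pre supplement and 90 mins, 120 mins, 180 mins and 210 mins post supplement". No other visit-day rule on food, training, caffeine or alcohol is stated.
- **Between visits.** Under Wash-out, section 8.1 says that in this period "the participants will be required to continue eating and training as per their usual routine".
- **Diet record.** Section 9.2: "Participants will be asked to record a 3 day diet recall using Easy Diet Diary (EDD) mobile app prior to their first lab visit". Section 8.1 expects this recall to help remove bias from irregular meals or extreme restriction.
- **Caffeine and alcohol.** Section 7.2 treats them as possible confounders, but only through limits on habitual use at entry.
- **Design and model.** Doses are 10, 20, 30 and 40 g with no 0 g visit (section 4.3). Order is counterbalanced by Latin square (section 8.1). Section 11.1 fits dose, period and their interaction as fixed effects and participant as a random effect; it names no diet, training or baseline covariate.

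**The concern.** The protocol says that protein and carbohydrate move its primary outcome, and then controls them on visit days with a fast alone. What is eaten before 14:30, and how long before, is left open. It may change from visit to visit, and no diet record is planned after visit 1.

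Two things are at stake. First, the pre-dose sample is the draw closest to that meal and is the natural reference for any rise. If the meal has shifted it, every change from baseline at that visit carries the shift. Second, in a crossover the dose contrasts rest on within-participant differences, so anything that varies between a participant's own visits goes straight into their error. With 16 participants that error matters. Information on meals and training that is not collected on the day cannot be recovered later.

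**Working it through.** **1. Clock times.** Inputs from section 8.1: food stops at 14:30 and arrival is at 17:00. The schedule figure suggests baseline at 17:15 and the drink at 17:30. A 17:30 drink fits the 3 h fast in section 11.3 (14:30 + 3 h) and the 21:00 finish in section 8.1 (17:30 + 210 min), so the two statements of the fast agree.

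Minimum time since food = sample time - 14:30:

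| Sample | Clock | Hours since food |
|---|---|---|
| Baseline | 17:15 | 2.75 |
| Drink | 17:30 | 3.0 |
| 90 min | 19:00 | 4.5 |
| 120 min | 19:30 | 5.0 |
| 180 min | 20:30 | 6.0 |
| 210 min | 21:00 | 6.5 |

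The protocol follows a protein drink for 210 min = 3.5 h. Used as a rough yardstick for a meal, 3.5 h covers the baseline sample but none of the post-dose samples. The exposure that the documents support is therefore mainly to the baseline, and through it to change from baseline.

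**2. What cancels and what does not.** Write the ratio at visit j, time t, as

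Y = participant + dose effect(t) + shared drift(t) + w(t) x m_j + error,

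where m_j is that visit's departure in meal or training, with variance s_m^2, and w(t) is how much of it is still acting.

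- *Dose A minus dose B, same participant, same t:* the shared drift drops out if it is additive. What remains is w(t) x (m_A - m_B). With balanced order and m unrelated to dose, its mean is zero and its variance is 2 x w(t)^2 x s_m^2. That is noise, not systematic bias.
- *Change from baseline:* the term becomes [w(t) - w(0)] x m_j. It is nonzero even if w(t) has fallen to zero by 90 min, because the baseline still carries w(0) x m_j.
- *Absolute rise and time course at one dose:* drift(t) - drift(0) stays in. Only a 0 g visit could separate it, and there is none.

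**3. Room for extra noise.** Section 11.4 states 85% power for a paired t-test with 16 participants, difference 0.024, root mean square error 0.05 and alpha 0.01. If 0.05 is the SD of the paired difference, the standardised effect is 0.024 / 0.05 = 0.48, the noncentrality is 0.48 x sqrt(16) = 1.92 on 15 df, and exact power is 19.4% two-sided (28.2% one-sided). If 0.05 is the within-participant SD, the SD of the difference is 0.05 x sqrt(2) = 0.0707, and power is 8.7% two-sided (13.8% one-sided). The 85% does not reproduce. That is a separate problem on which this point does not depend, but it shows how little slack there is.

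The documents do not say how much variance comes from meals or training, or whether 0.05 already includes it. Taking an assumed share k, SD of the difference = SD0 x sqrt(1 - k) if standardising removes it, or SD0 x sqrt(1 + k) if it comes on top. Power at n = 16, difference 0.024, two-sided 0.01:

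| Assumed share | 0.05 = SD of difference | 0.05 = within-participant SD |
|---|---|---|
| 50% removed | 43.7% | 19.4% |
| 25% removed | 27.5% | 12.0% |
| 10% removed | 22.1% | 9.7% |
| as stated | 19.4% | 8.7% |
| 10% added | 17.3% | 7.8% |
| 25% added | 14.9% | 6.8% |
| 50% added | 12.0% | 5.7% |

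These rows show sensitivity only; they do not estimate the meal effect.

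**The case against.** The case for leaving the plan alone has substance. The fast and the pre-dose sample are repeated at every visit. Dose order is counterbalanced. The entry criteria exclude heavy caffeine and alcohol users, and the diet recall is meant to find irregular eaters. The sentence on usual eating and training governs the wash-out days, so the visit-day gap rests on the absence of any other stated rule. The participant information and other appendices are not in the text at hand and might contain instructions. All of this stands, and it limits the point to baseline stability and noise.

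Three stronger readings are tempting and are not supported:

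- *That lunch distorts every post-dose curve because a 3 h fast is shorter than the 3.5 h of sampling.* By that yardstick all post-dose samples, at 4.5 h or more after food, lie outside it. The 210 min marks the end of sampling, not a demonstrated end of response, so a longer effect cannot be excluded; but it is not shown.
- *That a recovering ratio after lunch is counted as a rise due to ALAC at every dose.* This needs lunch to have lowered the ratio. Section 4.1 describes opposing mechanisms: other amino acids raise the competing LNAA, while insulin moves branched-chain amino acids into muscle. The direction is open.
- *That the drift can be expressed as a share of the 0.024 difference.* This needs a baseline ratio, a meal effect and a half-life, none of which the documents give. It also compares a shift common to all doses with a paired difference in which such a shift cancels.

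What the objections do not answer is that counterbalancing leaves the visit-to-visit noise in place, and that a recall taken before visit 1 says nothing about visits 2 to 4.

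**Conclusion.** The point holds as a conduct weakness that is cheap to repair. The protocol names diet as a source of bias and aims to exclude it, yet on visit days it relies on a fast of about 3 h and keeps no diet record after visit 1. The consequences are a pre-dose sample that may be shifted (about 2.75 h after the latest permitted food), avoidable within-participant noise in the dose contrasts, and, with no 0 g visit, a shared drift that cannot be separated from the absolute rise and time course. Systematic bias between doses is not expected under the counterbalanced order.

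Neither the size nor the direction can be derived from the documents. The conclusion assumes a drink at about 17:30; if the drink slips to 18:00 within the cannulation hour, each post-dose time since food lengthens by half an hour and the reasoning is unchanged. It also assumes that no visit-day instruction exists in appendices not shown.

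**What to change.** In section 8.1 (Intervention) and section 11.3, keep the fast as it is and add:

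1. Each participant records the last meal before visit 1, with content and clock time, and repeats the same meal at the same time before visits 2 to 4.
2. Training, caffeine and alcohol on the visit day are kept the same across the four visits.
3. Each visit day is logged in the Easy Diet Diary app already in use, with a note of training, and staff check the entry on arrival.
4. Deviations are recorded, and the visit is rescheduled where feasible.

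In section 9.2, extend the diet record from visit 1 to all four visits.

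Cost: an instruction sheet and at most four one-day entries per participant (16 x 4 = 64 in all), brief checking by staff, slight participant burden and an occasional rebooked evening visit. No samples or participants are added. The change steadies the baseline and lowers noise. It does not replace a 0 g visit for separating a shared drift from the absolute rise.
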